2 STUDY OBJECTIVES

The primary objective is to assess the efficacy of EYP-1901 compared to sham treatment in the improvement of moderately severe to severe NPDR.

The secondary objectives are:

- To characterize the safety of EYP-1901 in subjects with moderately severe to severe NPDR.

- To determine if EYP-1901 will prevent the worsening of diabetic retinopathy and reduce the incidence of DME.
- To evaluate the need for additional standard of care intervention due to ocular diabetic complications.
- To determine the anatomic effects of EYP-1901 in subjects with moderately severe to severe NPDR.
- To determine the systemic exposure to vorolanib and X-297, its main metabolite, measured through plasma levels up to Week 48.

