6.6.4 Permitted Medication and Procedures

Following the intravitreal injections of either dose of the EYP-1901 insert (2060 µg or 3090 µg) on Day 1, treatment of the fellow eye will be at the discretion of the Investigator. Any fellow eye therapy should be documented in concomitant meds during the study if required.

After Day 1, all subjects, regardless of treatment assignment, may receive approved anti-VEGF supplemental therapy or other standard of care therapy if they have ocular diabetic complications

warranting intervention. All ocular diabetic complications in the study eye will be managed in accordance with each study center's standard of care and must be documented as an AE.

During the study, participants who develop ocular diabetic complications in the study eye requiring anti-VEGF treatment per standard of care may be administered therapy as required. If needed, the study centers will provide their own supply of FDA-approved anti-VEGF therapy and submit the associated costs for reimbursement. The number of anti-VEGF injections received, the name of the product being injected, and the timing of all injections must be recorded in the source documents and eCRF.

Participants who develop ocular diabetic complications requiring PRP or retinal laser standard of care must have the time of laser treatment recorded in the source documents and eCRF.

Participants who develop ocular diabetic complications requiring surgical intervention standard of care (eg, pneumatic retinopexy, cryopexy, scleral buckle) must have the type of intervention and the time of intervention recorded in the source documents and eCRF.

In this case, the Investigator is required to contact the Medical Monitor prior to administering treatment if feasible.

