## **10.2. Secondary Efficacy Endpoint Analyses**

### Response Endpoints

The analysis and summarization performed for the primary endpoint ([Section 10.1](#)) will be repeated for the following secondary efficacy endpoints.

- Percentage of subjects improving ≥2 steps from baseline in the DRSS score in the study eye at Weeks 24 and 48.
- Percentage of subjects improving ≥2 steps from baseline in the DRSS score in the study eye at each timepoint (remaining timepoints apart from Weeks 24, 36, and 48)
- Percentage of subjects worsening ≥2 steps from baseline in the DRSS score in the study eye at each timepoint
- Percentage of subjects improving ≥3 steps from baseline in the DRSS score in the study eye at each timepoint
- Percentage of subjects worsening ≥3 steps from baseline in the DRSS score in the study eye at each timepoint
- Percentage of subjects who developed a vision-threatening complication due to diabetic retinopathy in the study eye through Week 24, through Week 36, and through Week 48.

Vision threatening complications due to diabetic retinopathy will be indicated by the presence of “Vitreous hemorrhage” or the presence of “Tractional retinal detachment” reported on the Ocular Examination – Dilated Ophthalmoscopy CRF (proliferative diabetic retinopathy [PDR] events, and “Neovascularization for the Iris” answered as “Yes” or “Neovascularization for the Angle” answered as “Yes” per the Ocular Examination - Slit Lamp Biomicroscopy CRF (anterior segment neovascularization [ASNV] events).

Summarization and analyses will be repeated for the following subgroups – baseline DRSS in the study eye of 43 (moderate NPDR), 47 (moderately severe NPDR), and 53 (severe NPDR), and baseline DRSS score in the study eye, categorical ( $\leq 47$ ,  $\geq 53$ ).

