**This document is confidential.**

- Percentage of subjects who developed CI-DME in the study eye through Week 24, through Week 36, and through Week 48.

The occurrence of a CI-DME event in the study eye will be identified via examination of centrally read custom algorithm CST data and adverse events. For the CST data at any given time point, if results are available for no more than 2 raters, the average value will be used, and if results are available for three raters, the median value will be used. CI-DME will have occurred when an adverse event occurs which has a mapped preferred term of 'Cystoid macular oedema', 'Diabetic retinal oedema', or 'Macular oedema', for which the temporally closest CST measurement is greater than or equal to 320 microns.

Two additional endpoints will also be summarized.

- Macular edema (Definition 1) will have occurred when an adverse event occurs which has a mapped preferred term of 'Cystoid macular oedema', 'Diabetic retinal oedema', or 'Macular oedema'.
- Macular edema (Definition 2) will have occurred when an adverse event occurs which has a mapped preferred term of 'Cystoid macular oedema', 'Diabetic retinal oedema', or 'Macular oedema', and which has treatment with a concomitant medication with a mapped preferred term of 'aflibercept', 'ranibizumab', 'bevacizumab', or 'faricimab'.

- Percentage of subjects who received anti-VEGF or additional standard of care intervention due to ocular diabetic complications in the study eye through Week 24, through Week 36, and through Week 48.

Anti-VEGF use is identified in reported concomitant medication data as those medications with ATC code 'S01LA'.

Unique mapped concomitant medication and procedure terms and associated information will be reviewed by masked ophthalmology team members to identify those mapped concomitant medication and procedure terms that indicate the use of additional standard of care intervention due to ocular diabetic complications.

- Percentage of subjects who received PRP in the study eye, inclusive of subjects undergoing vitrectomy with endo-laser, through Week 24, through Week 36, and through Week 48.

Unique mapped procedure terms and associated information will be reviewed by masked ophthalmology team members to identify those mapped procedure terms that indicate receipt of PRP.

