#### Time to Event Endpoints

Time (in weeks) to develop any vision threatening complication (PDR/ASNV) in the study eye through a particular time point (Week 24, Week 36, or Week 48) will be computed as the earliest date of a vision threatening complication in the study eye prior to the particular time point minus the date of study drug administration, plus 1 day, divided by 7 days per week. For subjects not experiencing a vision threatening complication in the study eye prior to the particular time point of interest, the subject will be censored at their date of discontinuation from the study (if prior to the time point of interest) or at the time point of interest.

Time (in weeks) to develop a CI-DME in the study eye, macular edema in the study eye per Definition 1, and macular edema in the study eye per Definition 2 will be computed in a similar manner.

This document is confidential.

Each time to event endpoint will be summarized with the number and percentage of subjects who experienced the endpoint, number and percentage of subjects who were censored, and Kaplan-Meier estimates of median and first and third quartiles. The EYP-1901 treatment arms will be compared to the sham IVT group using a log-rank test. A corresponding Kaplan-Meier plot will be prepared for the FAS only.

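### The intervention and PRP endpoints get only crude percentages with an unsettled denominator for early leavers, while sister endpoints get a censored analysis

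*SAP*

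**What the plan says.** Protocol 2 and SAP 3.2 name a secondary objective: "To evaluate the need for additional standard of care intervention due to ocular diabetic complications". Two endpoints serve it. One is "Percentage of subjects who received anti-VEGF or additional standard of care intervention due to ocular diabetic complications in the study eye through Week 24, through" (the list goes on to Weeks 36 and 48). The other is "Percentage of subjects who received PRP in the study eye, inclusive of subjects undergoing vitrectomy with endo-laser, through Week 24", with the same later time points. Both stand under Response Endpoints in SAP 10.2, where "The analysis and summarization performed for the primary endpoint" is to be repeated. In the readable part of SAP 10.1 that means counts, percentages and a Clopper-Pearson interval per arm. Some text in SAP 10 and 10.1 is redacted. The table index (14.2.13.x and 14.2.14.x) has percentage tables only, titled by follow-up visit and not as cumulative. The figure index has no Kaplan-Meier plot for either endpoint.

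PDR/ASNV and CI-DME are analysed twice, as percentages and as time to event. For a subject with no event, the time-to-event rule is that "the subject will be censored at their date of discontinuation from the study (if prior to the time point of interest) or at the time" (that is, the week in question). Kaplan-Meier quartiles and a log-rank test follow. Macular edema Definitions 1 and 2 get the same treatment. Definition 2 is an edema adverse event treated with a listed anti-VEGF drug.

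On denominators, SAP 8.3 says that missing data are generally not imputed. SAP 16.2.5.2 gives two defaults, subjects with an observation and subjects assessed. It warns that the choice can be difficult and leaves the details to footnotes. On dates, Protocol 6.6.4 requires that "the timing of all injections must be recorded in the source documents and eCRF", and also requires the time of laser and of surgical intervention.

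**The concern.** Both endpoints are cumulative. A subject who leaves at Week 12 without intervention has been observed for only a quarter of the 48 weeks. A percentage through Week 48 must either count that subject as free of intervention for time nobody observed, or remove the subject. The first choice understates an arm's cumulative risk. The second overstates it, because subjects treated before leaving stay in while untreated leavers go. The readable SAP does not say which applies.

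The study is descriptive, so the reported percentage is itself the result for this objective and should have one defined meaning. The treatment is also uneven. Definition 2, which the SAP added, has a censored analysis, while the protocol's own anti-VEGF endpoint has none although the dates are collected.

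**Working it through.** **Inputs from the documents.** About 20 subjects per arm (SAP 4.3). No intervention rate and no dropout rate is stated, so there is no figure of the plan to reproduce. All rates below are assumptions.

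**Effect of the denominator alone.** Take 20 treated subjects with 6 interventions and 4 event-free leavers. Keeping the leavers gives 6/20 = 30.0% (Clopper-Pearson 95% CI 11.9 to 54.3). Dropping them gives 6/16 = 37.5% (15.2 to 64.6).

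**Model.** Let p be the true 48-week intervention risk with constant hazard, and d the share of subjects assigned a leaving time, spread uniformly over Weeks 4 to 48.

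- Hazard per week: λ = −ln(1 − p)/48
- Mean probability of being event-free on leaving: S = [exp(−4λ) − exp(−48λ)]/(44λ)
- Leavers counted as event-free: C = (1 − d)p + d(1 − S)
- Event-free leavers: L = dS
- Leavers dropped: D = C/(1 − L)

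Sham, p = 0.30 and d = 0.25: λ = 0.00743, S = 0.828, C = 0.75 × 0.30 + 0.25 × 0.172 = 0.268, L = 0.207, D = 0.268/0.793 = 0.338.

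EYP-1901, p = 0.10 and d = 0.10: S = 0.945, C = 0.90 × 0.10 + 0.10 × 0.055 = 0.0955, L = 0.0945, D = 0.0955/0.9055 = 0.1055.

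**Dropout 25% sham, 10% EYP-1901.** Entries are sham minus EYP-1901 in percentage points, with differences taken before rounding.

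| True risks (difference) | Leavers counted event-free | Leavers dropped |
|---|---|---|
| 30 vs 10 (20) | 26.8 − 9.6 = 17.2 | 33.8 − 10.5 = 23.2 |
| 40 vs 10 (30) | 35.9 − 9.6 = 26.3 | 44.4 − 10.5 = 33.8 |
| 50 vs 15 (35) | 45.0 − 14.3 = 30.7 | 54.6 − 15.8 = 38.8 |
| 30 vs 30 (0) | 26.8 − 28.7 = −1.9 | 33.8 − 31.3 = +2.5 |

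The two readings err in opposite directions. In the first three rows they differ by about 6 to 8 points.

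**Dropout reversed, 10% sham and 25% EYP-1901.** With leavers counted as event-free, true differences of 20, 30 and 35 become 19.8, 29.5 and 34.7. The biases nearly cancel.

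**Second dropout model.** This uses constant, independent hazards for intervention and dropout, with true risks of 30% sham and 15% EYP-1901 (true difference 15.0).

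- Dropout 10% sham, 30% EYP-1901: 15.9 counted, 13.6 dropped.
- Dropout 30% sham, 10% EYP-1901: 11.2 counted, 18.5 dropped.
- Dropout 30% in both arms: 12.8 counted, 16.7 dropped. Equal dropout therefore still shifts a real effect.

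In 20,000 simulated trials per setting with 20 per arm, Kaplan-Meier with censoring at discontinuation gave a mean difference of 15.0 in both unequal-dropout settings. It was within 0.1 point of zero where the arms truly did not differ.

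**Sampling error for scale.** For 30% vs 10% with 20 per arm, √(0.30 × 0.70/20 + 0.10 × 0.90/20) = 0.122, or 12.2 points. In the simulations the SD of the difference was about 12 to 17 points across the methods.

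**The case against.** The strongest reply is that the SAP implements the protocol. Protocol 10 words both endpoints as percentages of subjects who received treatment, and reserves time to event for PDR/ASNV and CI-DME. That stands: the crude percentage is the protocol's endpoint and must stay. It does not supply the missing denominator, and it does not make the percentage an estimate of need through Week 48.

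A second reply is that the gap is partly covered. Definition 2 captures edema-driven anti-VEGF use with censoring, SAP 9.1 tabulates discontinuation by arm, and the PP Set repeats the analysis in subjects who reach Week 36. This helps only in part. Definition 2 omits PRP and intervention for other complications. Disposition tables reveal unequal dropout without correcting for it. The PP Set selects on retention and does not cover loss between Weeks 36 and 48. The LOCF tables in the index concern only the primary DRSS endpoint.

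Three stronger readings are tempting, and none is supported:

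- **A known direction of bias.** A reader might infer that more sham dropout shrinks the apparent benefit and more EYP-1901 dropout inflates it. The first reverses if leavers are dropped. The second fails at the assumed rates with 10% and 25% dropout, although it appears at 30% vs 15%.
- **Lost power.** The study is not formally powered, Protocol 11.3.7 calls all analysis descriptive, and no readable text plans a test on these percentages. A power comparison has no target here.
- **No rule anywhere.** SAP 16.2.5.2 has default denominators, and redacted text in SAP 10 and 10.1 could hold more. The supportable statement is that the readable text does not settle the matter.

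**Conclusion.** The point holds in a limited form. In the readable SAP, two cumulative endpoints for a stated secondary objective have only a percentage whose denominator is unsettled for event-free early leavers. Under either reading it is generally biased for the cumulative risk of intervention when subjects leave early. With assumed dropout of 25% and 10%, the shift is about 3 to 4 points for true differences of 20 to 35, and about 2 to 2.5 points where there is no true effect. Its sign depends on the denominator, the true rates and which arm loses more.

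The shift is well below the sampling SD, is no larger than one subject in an arm of 20 (5 points), and is zero without dropout. It affects how a secondary result is read. It does not affect the primary endpoint or any planned test of these percentages that can be read. The figures rest on constant hazards and on dropout unrelated to the risk of intervention.

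**What to change.** In SAP 10.2, under Time to Event Endpoints, add time to first study-eye anti-VEGF or additional standard-of-care intervention, and time to first study-eye PRP (including vitrectomy with endolaser). Use the recorded dates and the existing censoring rule. Report the Kaplan-Meier cumulative percentage with 95% CI by arm at Weeks 24, 36 and 48 beside the crude percentage. The existing rule gives only quartiles, so the fixed-week percentages must be specified.

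For the crude percentage, state that the FAS denominator is all FAS subjects in the arm, and label it as intervention received while under observation. Align the titles of Tables 14.2.13.x and 14.2.14.x with the cumulative wording of the text.

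**Cost.** No new data and no change to a protocol endpoint. Following the present index pattern (three time points, FAS and PP) means 6 tables and 3 figures per endpoint, so 12 tables and 6 figures. One analysis through Week 48, read at the three weeks, would need 2 endpoints × 2 sets = 4 tables and 2 FAS figures. Kaplan-Meier assumes non-informative dropout, which is a reason to keep the crude percentage alongside it.

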#### Time to Event Endpoints

Time (in weeks) to develop any vision threatening complication (PDR/ASNV) in the study eye through a particular time point (Week 24, Week 36, or Week 48) will be computed as the earliest date of a vision threatening complication in the study eye prior to the particular time point minus the date of study drug administration, plus 1 day, divided by 7 days per week. For subjects not experiencing a vision threatening complication in the study eye prior to the particular time point of interest, the subject will be censored at their date of discontinuation from the study (if prior to the time point of interest) or at the time point of interest.

Time (in weeks) to develop a CI-DME in the study eye, macular edema in the study eye per Definition 1, and macular edema in the study eye per Definition 2 will be computed in a similar manner.

This document is confidential.

Each time to event endpoint will be summarized with the number and percentage of subjects who experienced the endpoint, number and percentage of subjects who were censored, and Kaplan-Meier estimates of median and first and third quartiles. The EYP-1901 treatment arms will be compared to the sham IVT group using a log-rank test. A corresponding Kaplan-Meier plot will be prepared for the FAS only.

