### **5.2. Secondary Efficacy Endpoints**

The secondary objectives will be assessed with the following secondary endpoints in each EYP-1901 dose level versus the sham IVT injection group:

- Percentage of subjects improving  $\geq 2$  steps from baseline in the DRSS score in the study eye at Weeks 24 and 48 in each EYP-1901 dose level versus the sham IVT injection group.
- Percentage of subjects improving  $\geq 2$  steps or  $\geq 3$  steps over time in DRSS score in the study eye from baseline.
- Percentage of subjects worsening  $\geq 2$  steps or  $\geq 3$  steps over time in DRSS score in the study eye from baseline.
- Percentage of subjects who developed a vision-threatening complication due to diabetic retinopathy in the study eye at Weeks 24, 36, and 48.
- Percentage of subjects who developed CI-DME in the study eye at Weeks 24, 36, and 48.
- Time to develop any neovascular vision threatening complication (PDR/ASNV) in the study eye through Weeks 24, 36, and 48.
- Time to develop CI-DME in the study eye through Weeks 24, 36, and 48.
- Percentage of subjects who received anti-VEGF or additional standard of care intervention due to ocular diabetic complications in the study eye at Weeks 24, 36, and 48.
- Percentage of subjects who received PRP in the study eye, inclusive of subjects undergoing vitrectomy with endolaser, at Weeks 24, 36, and 48.
- Area under the curve (AUC) for change from baseline in BCVA in the study eye at Weeks 24, 36, and 48.

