#### 8.4. Visit Windows

Safety and efficacy data will be analyzed per study visit. The named visit as recorded in the electronic Case Report Form (eCRF) will be displayed. Pre-specified visit windows are given in [Table 2](#).

Table 2: Visit Windows for Endpoints Collected at All Visits

Visit	Target Study Day	Time Window	Visit Windows for Analysis
Screening	-21 to -5	NA	
Day 1	1	N/A	
Week 4	28	± 5 days	Study Days 2 to 56
Week 12	84	± 5 days	Study Days 57 to 126
Week 24	168	± 5 days	Study Days 127 to 210
Week 36	252	± 5 days	Study Days 211 to 294
Week 48	336	± 5 days	Study Days 295 to 350

This document is confidential.

Visit windows to be used for endpoints not collected at every visit are presented in [Table 3](#), [Table 4](#), and [Table 5](#).

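### Time to PDR/ASNV runs through Weeks 24, 36 and 48 but counts only events before an undated time point, so a complication first found at the named visit may be censored

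*SAP*

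**What the plan says.** SAP 5.2 lists the secondary endpoint as "Time to develop any neovascular vision threatening complication (PDR/ASNV) in the study eye through Weeks 24, 36, and 48".

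The time-to-event part of SAP 10.2 repeats *through* and then computes the time from the first complication dated before the time point: it "will be computed as the earliest date of a vision threatening complication in the study eye prior to the particular time point", counted in weeks from dosing. Subjects without such an event are "censored at their date of discontinuation from the study (if prior to the time point of interest) or at the time point of interest". The time point is named only as a week. No study day, visit date or window end is attached to it. CI-DME, macular edema by Definition 1, and "macular edema in the study eye per Definition 2 will be computed in a similar manner".

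The events come from the dilated ophthalmoscopy form and from the "Slit Lamp Biomicroscopy CRF (anterior segment neovascularization [ASNV] events"), so their dates are mainly visit dates. The matching percentage endpoint uses the same complications "in the study eye through Week 24, through Week 36, and through Week 48", again without a cut-off day.

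SAP 8.4 says "Safety and efficacy data will be analyzed per study visit". Its Table 2 gives target days 168, 252 and 336, with analysis windows ending on Days 210, 294 and 350; for Week 48 the window is "Study Days 295 to 350". The time-to-event text does not refer to these days. Protocol 5.1 and SAP Table 1 allow visits within ±7 days, while SAP Table 2 shows ±5 days.

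**The concern.** *Through* a week includes it; *prior to* a time point excludes it. For a continuously observed event the difference would be trivial. Here detection is tied to examinations, and the examination that defines the week is the one at the boundary. The schedule has no visit between Week 36 and Week 48. Unless there is an unscheduled or early-termination visit, a complication arising in those 12 weeks is therefore first recorded at the Week 48 visit.

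Two programmers could follow SAP 10.2 faithfully and count different events. On two of the three natural readings, a complication observed at a permitted visit becomes a censored observation in the Kaplan-Meier estimates and the log-rank comparisons with sham.

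There is a smaller related gap. An event-free subject is carried to the time point or to the discontinuation date, even if the last eye examination was earlier.

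**Working it through.** The plan gives no event rate, event count or power figure for this endpoint, so there is nothing of that kind to reproduce. The check is a count of days.

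**Inputs.** Dosing is Study Day 1 (SAP 8.2). Target days are 168, 252 and 336, and analysis windows end on Days 210, 294 and 350 (SAP Table 2). Visit windows are ±7 days (Protocol 5.1, SAP Table 1) and ±5 days (SAP Table 2).

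**Time scale.** SAP time = (event date − dosing date + 1)/7 = Study Day/7. This gives 168/7 = 24.0, 252/7 = 36.0 and 336/7 = 48.0 weeks, so the target days are exactly the nominal weeks.

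**Permitted visit days.** With ±7: Days 161–175, 245–259 and 329–343, which is 15 days each. With ±5: Days 163–173, 247–257 and 331–341, which is 11 days each.

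**Days on which a newly detected complication counts** (the same at all three weeks):

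| Time point taken as | ±7 days | ±5 days |
|---|---|---|
| Target day, strictly before | 7 of 15 | 5 of 11 |
| Target day, inclusive | 8 of 15 | 6 of 11 |
| End of analysis window | 15 of 15 | 11 of 11 |
| Subject's own visit date, strictly before | none | none |

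The window-end row holds even with strict wording, because the last permitted days fall earlier: 175 < 210, 259 < 294, 343 < 350.

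**Split on the target-day reading.** With ±7, 8 of 15 days fail (53%). One (1/15 = 7%) fails because of *prior to*, and seven (7/15 = 47%) fail because the horizon is fixed at the target day. With ±5, 6 of 11 fail, split 1 and 5.

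**What is recovered later.** Findings on Days 168–175 precede Day 252 and enter the Week 36 analysis. Findings on Days 252–259 precede Day 336 and enter the Week 48 analysis. Findings on Days 336–343 have no later horizon. The visit-date reading behaves the same way: Week 24 and Week 36 findings re-enter, Week 48 findings do not.

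**Outputs affected.** PDR/ASNV has 6 tables (14.2.7.1 to 14.2.9.2) and 3 Kaplan-Meier figures (14.2.1.1 to 14.2.1.3). CI-DME has another 6 tables (14.2.10.1 to 14.2.12.2) and 3 figures (14.2.2.1 to 14.2.2.3). The Week 48 part, where an omission is permanent, is 2 tables and 1 figure for each endpoint.

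**The case against.** The strongest reply is that the plan's intention is clear enough. The defining sentence itself says *through*, SAP 8.4 makes by-visit analysis the general rule, and nothing says that the time point is the target day. Censoring at a fixed day is also an ordinary Kaplan-Meier choice: a complication dated Day 172 does fall after Week 24. Much of this stands. The harm depends on the reading, and the window-end reading has none. What remains is that the operative sentence states a strict rule, and nothing in the plan selects the harmless reading.

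Three stronger inferences are tempting and should not be drawn.

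- A reader might take 8 of 15 days as a prediction that about half of the complications found around each visit are lost. It is a count of days on one assumed reading, 7 of the 8 come from the assumed horizon, and the documents give no event rate or distribution of visit dates.
- A reader might infer that the Kaplan-Meier tables will contradict the percentage tables. The percentage endpoints have no stated cut-off day either, and the primary analysis they repeat (SAP 10.1) contains redactions. A mismatch is possible but not established.
- A reader might infer the same loss for CI-DME and macular edema. Those events are identified from adverse events, whose onset dates need not be visit dates. They inherit the undefined cut-off, not necessarily the loss.

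The censoring gap is also narrow. Early-termination visits call for ophthalmoscopy and slit-lamp examination, so the discontinuation date should usually lie close to the last examination.

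**Conclusion.** The inconsistency is real and minor. SAP 10.2 excludes events at a boundary that the endpoint definition includes, and it leaves that boundary undated. The lasting consequence is confined to complications first found at the Week 48 visit: any such visit on the visit-date reading, or one held on or after Day 336 on the target-day reading. They would enter no Kaplan-Meier or log-rank output, although the examination summaries in SAP 11.6 would still show them.

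The conclusion assumes that events are dated at examinations, which follows from the case-report forms named in SAP 10.2, and that one of those two readings is programmed. With about 20 subjects per arm, one omitted event is 1/20 = 5 percentage points of that arm, but this reflects the arm size and is not an estimate of loss. The endpoints are secondary, the study is not powered for testing, the rule is the same in all arms, and the primary endpoint is untouched.

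**What to change.** In SAP 10.2, replace *prior to* with *on or before*, and state that the named visit's examination counts. One way is an inclusive cut-off at the last permitted visit day: Day 175, 259 or 343 under ±7 days. The ±7 and ±5 day windows must be reconciled first; under ±5 the corresponding days would be 173, 257 and 341.

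Use the same cut-off for the matching percentage endpoints and for the adverse-event onset dates behind CI-DME and macular edema. Censor event-free subjects at the last study-eye examination (PDR/ASNV) or the last study visit (adverse-event endpoints) on or before the cut-off.

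The ends of the analysis windows are a less suitable cut-off. Days 210 and 294 are 30.0 and 42.0 weeks (210/7, 294/7), so events up to six weeks later would appear under titles naming Weeks 24 and 36. Day 294 also reaches past the data sure to exist at the Week 36 snapshot described in SAP 13.

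The cost is one date condition and a few sentences. The horizon runs up to one week past the nominal week (175/7 = 25.0, 259/7 = 37.0, 343/7 = 49.0), which a footnote can state. Visits later than the permitted window stay outside that week's analysis.
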